8.1.3. Patient Reported Outcome Measures for AD

Every effort should be made for the participant to complete all patient reported outcome (PRO) questionnaires before any other evaluations. The amount of time required for participants to complete the PRO questionnaires is approximately 10-30 minutes (depending on the visit and associated PROs). The PROs should be checked for completeness by the study site staff at every in-clinic visit.

Participants will be provided a handheld device (provided by the Sponsor) for dosing diary and electronic patient-reported-outcomes (ePROs) or paper versions of the above to be completed at home as per the time points defined in the [SoA](#). The clinic sites may use paper versions of PROs.

The following PROs will be completed only on study visit days identified in [SoA](#), CCI

PP-NRS will be used by participants for daily completion of PROs at home, starting from the screening visit or at least 7 days prior to the dosing/randomization day (Day 1) and as defined in the [SoA](#).

All participants will complete PROs at follow-up visit in clinic.

Delegated site staff will monitor completion of PROs for adherence and will review adherence with participants at each visit and counsel as appropriate. If a participant has repeated non-adherence, the participant should be retrained on use of the device or filling out paper versions. If a participant is unable to complete ePROs due to documented technical issue or disability or other limitation, the participant will be permitted to enter or remain in the study providing that a valid alternate source of daily data entry is completed and reviewed by investigational site staff. No protocol deviations will be recorded in regard to PRO completion adherence. In the event of electronic malfunction of an ePRO or misplacement of paper versions of the PROs, a replacement device or paper PROs will be shipped to the site.

8.1.3.1. Peak Pruritus Numerical Rating Scale (PP-NRS) for AD

The PP-NRS is a daily patient-reported assessment of intensity of pruritus on an 11-point numerical rating scale, ranging from 0 ('No Itch') to 10 ('Worst Itch Imaginable') with a 24-hour recall period.² The PP-NRS will be completed once daily at least 7 days prior to Day 1, and completed once daily every day from Day 1 to Week 6 before IP dose is applied preferably at the same time of each day if applicable, as noted in the [SoA](#). Note that PP-NRS will be assessed daily during the 7 days immediately preceding randomization and a minimum of 4 daily scores out of the 7 days prior to Day 1 is required to calculate the baseline average score.

CCI

CCI

EFFICACY ASSESSMENTS FOR PSORIASIS

All efficacy assessments of psoriatic skin will be based only on areas treated with IP and excluding scalp, palms, soles, nails from the assessment/scoring.

8.1.4. Physician Assessments for Psoriasis

8.1.4.1. Psoriasis Area and Severity Index (PASI)

PASI quantifies the severity of a participant's psoriasis based on both lesion severity and the percentage of body surface area affected.¹¹

Lesion Severity Score

The basic characteristics of psoriatic lesions (erythema, induration and scaling) provide a means for assessing the severity of lesions. Assessment of these three main signs is performed separately for four areas of the body: head, upper limbs, trunk, and lower limbs. Average erythema, induration and scaling are rated for each body area according to a 5-point scale: 0, no involvement; 1, slight; 2, moderate; 3, marked; 4, very marked. Appropriate morphologic descriptors for each severity score are shown in [Table 10](#).

Table 10. Component Scoring Criteria for PASI*

Component Score		Description
Erythema (E)		
0	No involvement	None; may have residual hyperpigmentation
1	Slight	Pink or light red
2	Moderate	Darker pink-red
3	Marked	Red
4	Very Marked	Extremely red, “beefy” red
Induration (I)		
0	No involvement	None
1	Slight	Minimal elevation relative to normal surrounding skin
2	Moderate	Easily palpable with rounded edges
3	Marked	Elevated with hard, sharp borders
4	Very Marked	Very elevated with very hard, sharp borders
Scaling (S)		
0	No involvement	None
1	Slight	Mainly fine scale, some lesion partially covered
2	Moderate	Coarser thin scale, most lesions partially covered
3	Marked	Coarser thick scale, nearly all lesions covered, rough
4	Very Marked	Very thick scale, all lesions covered, very rough

* The PASI will exclude scalp, palms, soles, nails from the assessment/scoring.

BSA with Psoriasis for PASI Assessment (excluding scalp, palms, soles and nails)

BSA affected by psoriasis should be calculated in each of the four body regions ie, head and neck (h), upper extremities (u), trunk (t), and lower extremities (l). The area within each body region with the key signs of the disease is estimated using handprint as a measure, where the full palmar hand of the participant (ie, the participant’s fully extended palm, fingers and thumb together) represents approximately 1% of the total BSA.

Each region is typically assigned proportionate body surface areas of 10 (h), 20 (u), 30 (t), and 40 (l) handprints respectively. Refer to Table 11 to identify the surface area equivalent of 1 handprint in each respective body region.

Table 11. Handprint Determination of Body Region Surface Area for Psoriasis

Body Region	Total Number of Handprints in Body Region	Surface Area of Body Region Equivalent of One Handprint
Head and Neck	10	10%
Upper Limbs	20	5%
Trunk (including axillae and groin)	30	3.33%
Lower Limbs (including buttocks)	40	2.5%

Area Score

The extent (%) to which each of the four body regions is involved with psoriasis (by using Table 11 above) is categorized using a non-linear scaling method to a numerical area score according to the following BSA scoring criteria (Table 12).

Table 12. PASI Area Score Criteria

Percent BSA with psoriasis in a Body Region	Area Score
0%	0
>0-<10%	1
10-<30%	2
30-<50%	3
50-<70%	4
70-<90%	5
90-100%	6

Body Region Weighting

Each body region is weighted according to its approximate percentage of the whole body (Table 13).

Table 13. PASI Body Region Weighting

Body Region	Body Region Weighting
Head and Neck	0.1
Upper Limbs	0.2
Trunk (including axillae and groin)	0.3
Lower Limbs (including buttocks)	0.4

Calculating of PASI score

In each body region, the sum of the Severity Scores for erythema, induration and scaling is multiplied by the Area Score and by the Body Region Weighting to provide a body region value, which is then summed across all four body regions resulting in a PASI score as described in the following equation:

$$\text{PASI} = 0.1A_h(E_h+I_h+S_h) + 0.2A_u(E_u+I_u+S_u) + 0.3A_t(E_t+I_t+S_t) + 0.4A_l(E_l+I_l+S_l)$$

A = Area Score; E = erythema; I = induration/papulation; S=scaling; h = head and neck; u = upper limbs; t = trunk; l = lower limbs.

The PASI score can vary in increments of 0.1 and range from 0.0 to 72.0*, with higher scores representing greater severity of psoriasis.

*Since the scalp, palms, soles and nails will be excluded from the PASI assessment in this study (even if palms and soles are being treated with the IP), the maximum possible score will be less than 72.0.

8.1.4.2. Physician Global Assessment

The Physician Global Assessment (PGA) of psoriasis is scored on a descriptive 5-point scale.¹² The 5-point scale for PGA is: 0, “clear”; 1, “almost clear”; 2, “mild”; 3, “moderate”; 4 “severe” (Table 14). The assessment will be a static evaluation without regard to the score at a previous visit.

Table 14. Physician Global Assessment (PGA) Score

Physician’s Global Assessment		Description
0	Clear	No signs of psoriasis; post-inflammatory hyperpigmentation may be present
1	Almost Clear	No thickening; normal to pink coloration; no to minimal focal scaling
2	Mild	Just detectable to mild thickening; pink to light red coloration; predominantly fine scaling
3	Moderate	Clearly distinguishable to moderate thickening; dull to bright red, clearly distinguishable to moderate thickening; moderate scaling
4	Severe	Severe thickening with hard edges; bright to deep dark red coloration; severe/coarse scaling covering almost all or all lesions

8.1.4.3. BSA with Psoriasis

Assessment of body surface area (BSA) involved in psoriasis is performed separately for four areas of the body: head (including neck), upper limbs, trunk (including axillae and groin), and lower limbs (including buttocks). The percentage surface area affected by psoriasis is estimated by means of the “handprint method”, where the full hand of the participant (ie, the participant’s fully extended palm, fingers and thumb together) represents approximately 1% of the total BSA. Refer to Table 11 to identify the surface area equivalent of 1 handprint in each respective body region.

Body region value is then summed across all four body regions resulting in a total BSA with psoriasis as described in the following equation:

$$BSA (\%) = 0.1Sh + 0.2Su + 0.3St + 0.4Sl$$

where S = body region surface area with psoriasis; h = head & neck; u = upper limbs; t = trunk; l = lower limbs.

BSA with Psoriasis for Efficacy Assessment (Efficacy BSA)

BSA with psoriasis for efficacy evaluation excludes scalp, palms, soles, and nails.

BSA with Psoriasis for IP Need (Treatable BSA)

Evaluation of BSA for IP need is the total BSA across all body locations being treated with the IP. BSA for IP need evaluation method will be the same as the BSA with psoriasis for efficacy assessment, except that the BSA for IP need will include psoriasis on all IP treated body locations (including palms and soles but not scalp and nails). If a participant has

psoriasis on palms, and/or soles, these body locations will be included in the BSA for IP need estimation.

Investigational product should be applied to the BSA determined at Day 1 throughout the treatment period regardless of clearing or improvement of psoriasis. Any new psoriasis on treatment-eligible locations occurring following Day 1 should also be treated with the IP. Therefore, the BSA for IP need at subsequent visits should be equal to or greater than the value at Day 1.

A checklist of body site areas currently affected by psoriasis (body map) will be completed at the Day 1 visit. The body map will be reviewed at every visit to the site to update for any new, treatable areas, if needed.

8.1.5. Patient Reported Outcome Measures for Psoriasis

Every effort should be made for the participant to complete all patient reported outcome (PRO) questionnaires before any other evaluations. The amount of time required for participants to complete the PRO questionnaires is approximately 10-30 minutes (depending on the visit and associated PROs). The PROs should be checked for completeness by the study site staff at every in-clinic visit.

Participants will be provided a handheld device (provided by the Sponsor) for dosing diary and electronic patient-reported-outcomes (ePROs) or paper versions of the above to be completed at home as per the time points defined in [SoA](#). The clinic sites may use paper versions of PROs.

The following PROs will be completed only on study visit days identified in [SoA](#), CCI PSI will be used by participants for daily completion of PROs at home, starting from the screening visit or at least 7 days prior to the dosing/randomization day (Day 1) and as defined in the [SoA](#).

8.1.5.1. Psoriasis Symptom Inventory (PSI) for Psoriasis

PSI is a self-administered 8 item questionnaire that measures the severity of psoriasis symptoms over the past 24 hours and the past 7 days.¹³ The PSI will be completed once daily at least 7 days prior to Day 1 using a recall period of 24 hours. For the first 2 weeks up to Week 2 visit (inclusive), the PSI will also be administered daily using a recall period of 24 hours. After Week 2 visit, the PSI will be administered according to the [SoA](#) using a recall period of past 7 days. The measure includes concepts of itch, pain, burning, stinging, cracking, scaling, flaking, and redness. Patients are asked to respond to each item using a 5-point Likert response scale: 0: not all severe, 1: mild, 2: moderate, 3: severe and 4: very severe.

CCI

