9.4.2. Efficacy Analyses for Psoriasis

Endpoint	Statistical Analysis Methods
Primary: Change from Baseline PASI at Week 6	A landmark analysis using analysis of covariance of change from baseline PASI, adjusting for the baseline PASI score, to estimate the effect of the initially randomized treatment in the absence of prohibited medication regardless of treatment compliance. The analysis will use the mITT analysis set. Missing data due to any cause including censoring due to initiation of prohibited medication will be imputed using the corresponding vehicle arm, missing data in a vehicle arm will be imputed using data from the vehicle arm assuming data are missing at random (MAR). The analysis will combine the results from the multiple imputations using Rubin's rule as implemented in SAS PROC MIANALYZE.
Secondary: PGA Response at Week 6	A landmark analysis of the composite endpoint; achieving a PGA response (a score of clear (0) or almost clear (1) and ≥ 2 point improvement from baseline) without prohibited medication, while remaining on study and providing data. The analysis will use the mITT analysis set. Based on the definition of the composite endpoint all participants in the mITT set will have a response for all visits (ie, there is no missing data). The proportions responding and the risk difference between treated arms and their corresponding vehicle control arm will be analyzed using an unconditional exact method: risk differences and corresponding 2-sided unconditional exact 90% confidence intervals will be computed using the

Endpoint	Statistical Analysis Methods
	Chan and Zhang (1999) ¹⁶ method.

CCI

Other continuous secondary endpoints at time points specified in the SoA including: absolute PASI, change from baseline PASI, percent change from baseline PASI, absolute and change from baseline Itch Severity Score, absolute and change from baseline Psoriasis Symptom Inventory will be analyzed as described for the primary estimand along with descriptive statistics and possibly graphical displays.

Other binary secondary endpoints at time points specified in the SoA including, CCI PASI 75, CCI PGA of clear or almost clear will be analyzed as described for the secondary estimand along with descriptive statistics and possibly graphical displays.

CCI

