#### **For Psoriasis:**

- *Proportion of participants with PGA score clear (0) or almost clear (1) (on a 5-point scale) and  $\geq 2$  points improvement from baseline at Week 6 and other study visit time points specified in the SoA.*
- *Proportion of participants achieving PASI 75 (75% or greater improvement from baseline) at study visit time points specified in the SoA.*

- *Proportion of participants who achieved a Psoriasis Symptoms Inventory (PSI) score of 0 (not at all) or 1 (mild) on every item at study visit time points specified in the SoA.*
- *Change from baseline in PASI scores at study visit time points specified in the SoA (except Week 6).*
- *Percent change from baseline in PASI scores at study visit time points specified in the SoA.*
- *Proportion of participants with PGA score clear (0) or almost clear (1) and  $\geq 2$  points improvement from baseline at time points specified in the SoA.*
- *Percent change from baseline in BSA at study visit time points specified in the SoA.*
- *Incidence of treatment emergent adverse events (AEs) and serious adverse events (SAEs), clinically significant changes in vital signs, electrocardiogram (ECG), and laboratory tests.*
- *Incidence of severity grades in skin tolerability at times indicated in SoA.*

CCI

CCI

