### 3.4. Baseline Variables

In general, for all analyses, baseline will be defined based on observations collected prior to first dose. Baseline values for demographics and height will be based on measures collected at Visit 1/Screening visit. Study Day 1 is defined as the day the subject receives first dose of study drug. For purposes of all other analyses including analyses for change from baseline, the baseline value will be defined as the last measurement before first dose on Day 1. If a value is missing on Day 1, then the last available observation

before Day 1 will be used. For the PP-NRS score, baseline will be defined as the average of all values recorded between Day -7 and Day -1.

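### PSI recall changes from 24 hours to 7 days after Week 2 with no visible bridge, so PSI change from baseline and the response time course mix two recall versions

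*Protocol*

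**What the plan says.** Protocol 8.1.5.1 sets the collection in three steps. Before dosing, "The PSI will be completed once daily at least 7 days prior to Day 1 using a recall period of 24 hours". Next, "For the first 2 weeks up to Week 2 visit (inclusive), the PSI will also be administered daily using a recall period of 24 hours". Finally, "After Week 2 visit, the PSI will be administered according to the" SoA, "using a recall period of past 7 days". In the psoriasis SoA (Protocol 1.3.2) the scheduled visits after Week 2 are Week 4, Week 6 and Follow-up.

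Three planned uses of the PSI matter here:

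- **Responder endpoint.** A secondary endpoint at SoA visits (Protocol 3.2, SAP 3.2): "Proportion of participants who achieved a Psoriasis Symptoms Inventory (PSI) score of 0 (not at all) or 1 (mild) on every item". SAP 6.2.2 analyses it like the IGA/PGA response, with the Chan and Zhang method.
- **Time course.** SAP 5.2.1 graphs the response rate of every binary endpoint over time for each arm.
- **Continuous PSI.** Protocol 9.4.2 states that "absolute and change from baseline Psoriasis Symptom Inventory will be analyzed as described for the primary estimand", at SoA time points. The visible list of continuous secondary endpoints in SAP 6.2.3 does not include it.

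On baseline, SAP 3.4 averages Day -7 to Day -1 for PP-NRS only. For other measures, "the baseline value will be defined as the last measurement before first dose on Day 1".

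**The concern.** A 24-hour score and a 7-day score answer different questions about the same symptoms. A participant whose disease is stable but varies from day to day may score differently on the two. When the version changes between Week 2 and Week 4, any step in the PSI curve at that point may be drug effect, disease course or the change of recall, and the data as planned cannot separate them. A true plateau could look like lost response.

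The same mismatch enters change from baseline at Weeks 4 and 6, because no 7-day PSI is scheduled before dosing. The baseline is also a single day's entry although at least seven daily entries are planned. At stake is how the onset and maintenance of symptom response is read in the compound's first study in psoriasis. The SAP amendment itself treats the longitudinal profile of PGA response as clinically important.

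**Working it through.** The documents give no sample size, power or effect size for PSI, so there is no planned figure to reproduce.

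**1. Recall version by time point** (Protocol 8.1.5.1 read against Protocol 1.3.2)

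| Time point | Recall |
|---|---|
| Daily, at least 7 days before Day 1 | 24 hours |
| Daily, through the Week 2 visit | 24 hours |
| Week 4, Week 6, Follow-up | 7 days |

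**2. Change from baseline.** Under the SAP 3.4 default, the change at Week 4 or 6 is a 7-day score minus one 24-hour score. It equals the true change, plus any shift due to the recall form, minus the day-specific error in the baseline. The last two terms do not cancel within an arm.

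**3. Between-arm contrast.** The responder endpoint is an absolute state with no baseline term, both arms change version at the same visit, and Chan and Zhang uses no covariate. The comparison at a given visit therefore uses one version. For a baseline-adjusted ANCOVA, let Y be the follow-up score, B baseline and T treatment. The model Y - B = a + tT + bB + e is the same as Y = a + tT + (b + 1)B + e. The treatment effect t is identical, so the recall form of B does not bias it. It affects only how much variance B explains.

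**4. Precision.** Assume independent day-to-day error and a day-to-day intraclass correlation (ICC) r of 0.60 to 0.90. The reliability of one day is r and that of a 7-day mean is 7r/(1 + 6r).

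- r = 0.60: 4.2/4.6 = 0.913; ratio to one day 0.913/0.60 = 1.52.
- r = 0.90: 6.3/6.4 = 0.984; ratio 0.984/0.90 = 1.09.

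The squared correlation of baseline with follow-up scales with reliability, so averaging would raise it by a factor of 1.09 to 1.52. The effect on the standard error depends on the underlying correlation, which the documents do not give.

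**5. Time course (illustration).** A simulation of 400,000 participants with no change in disease takes the worst-item score as a unit-variance normal variable with assumed ICC 0.60, 0.75 or 0.90. The cut-off is set to give the 24-hour responder rate in the first column.

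| 24-hour rate | 7-day form answered as weekly average (ICC 0.60 / 0.75 / 0.90) | Answered for the worst day (ICC 0.60 / 0.75 / 0.90) |
|---|---|---|
| 20% | 15.0 / 17.0 / 18.9% | 2.5 / 4.9 / 9.5% |
| 40% | 37.7 / 38.9 / 39.5% | 10.0 / 15.7 / 24.1% |
| 60% | 62.2 / 61.1 / 60.3% | 24.5 / 32.4 / 42.7% |

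With weekly-average answering the shift runs from -5.0 points (15.0 - 20) to +2.2 points (62.2 - 60). With worst-day answering the fall runs from 10.5 points (20 - 9.5) to 35.5 points (60 - 24.5).

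**The case against.** The strongest reply is that the PRO objective is a comparison with vehicle, and that comparison is sound at each visit. This stands. A reader might infer that the Week 6 PSI responder result is biased; step 3 shows that it is not. Nor does any formal decision rest on PSI, since SAP 5.1 confines inference to EASI and PASI.

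Second, PSI change from baseline appears in Protocol 9.4.2 but not in the Protocol 3.2 objectives table, SAP 3.2 or the visible SAP 6.2.3 list. The SAP may modify the protocol here, so the analysis may have been dropped. This also stands, but the documents do not say so, and the responder plot remains either way.

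Third, text after Protocol 8.1.5.1 and in SAP Appendix 3 is redacted and may hold PSI scoring rules. Single-day scoring at Weeks 1 and 2 is therefore not established. The single-day baseline is the reading the visible default gives, although SAP 3.4 does not name PSI. The collection schedule itself is visible.

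Fourth, the protocol presents both recall periods as forms of one instrument. It is too strong to call them different instruments. It is equally unsupported to treat them as interchangeable, because nothing visible says they are.

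Lastly, a reader might compute that someone with 90% good days falls from a 0.90 chance of response to 0.9^7 = 0.478. That needs both worst-day answering and independent days. With perfectly correlated days the chance stays at 0.90. The documents support neither assumption.

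**Conclusion.** The point holds in a limited form. As visibly written, the plan mixes recall versions in within-participant PSI change at Weeks 4 and 6 and in the response profile across Week 2 to Week 4, and it leaves precision unused in any baseline-adjusted PSI analysis. It does not bias the randomised comparison at any single visit and does not touch the primary endpoints.

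The size cannot be determined from the documents. The range in step 5, from a few points in either direction to a fall of about 35 points, rests on an assumed normal severity variable, an assumed ICC of 0.60 to 0.90, and two assumed ways of answering a 7-day question. The conclusion also assumes that no redacted rule already bridges the versions. That uncertainty is the reason to settle the handling before the data are read; it is not evidence of a large effect.

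**What to change.** In SAP 3.4 and the PSI derivation:

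- Define PSI baseline as the 7-day average of each daily item score from Day -7 to Day -1, with at least 4 of 7 days present. SAP 3.4 and Protocol 8.1.3.1 already do this for PP-NRS.
- Derive the Week 1 and Week 2 visit scores as the average of the preceding 7 daily scores, also with a minimum number of days. State that only post-dose entries count, because a Week 1 visit at Day 6 (Day 8 - 2) would otherwise reach back before Day 1.
- State how an averaged item, which need not be a whole number, is judged against the 0-or-1 rule, for example an average of at most 1.
- Label the recall version, or break the line between Week 2 and Week 4, in by-visit displays. State that a step there is not interpreted as change in disease.
- State whether the PSI change from baseline in Protocol 9.4.2 is still planned.

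The cost is a few SAP sentences and one derivation, with no new data collection. The downside is that averaging daily scores reduces the mismatch without making the two forms identical.

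Optionally, add one 7-day-recall PSI at Day 1 before dosing. This gives a like-for-like baseline for Weeks 4 and 6, at the cost of a small added burden and possible carry-over between forms completed close together.
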